## 4.2 ANALYSIS POPULATIONS

Given the impact of the early findings from the starting doses on the actual doses regimens implemented in the trial, on the final treatment classification required for summary purposes and on the identification of the appropriate dataset to estimate the treatment comparison, the following populations are considered in order to provide an exhaustive reporting of this study data.

#### **4.2.1         Safety Population**

- Safety Global

The “Safety Global” population consists of all subjects who gave informed consent and received at least one dose of study medication, whether prematurely withdrawn from the study or not.

Data will be summarized according to treatment classified as derived from PK exposure: Placebo, Low Tertile, Medium Tertile, High Tertile and All Treated with Active.

- Safety Inferential

The “Safety Inferential” population consists of the subset of the “Safety Global” population that is identified to address the primary efficacy study objective.

Data will be summarized according to treatment classified as: Placebo, 10mg equivalent.

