6.3 ANALYSIS POPULATIONS

6.3.1 Safety Analysis Population

All subjects who have received at least one dose of the study medication, whether prematurely withdrawn from the study or not, will be included in the safety analysis population. Data will be analyzed according to the treatment as randomized. Any dosing error will be reviewed and the implications of such errors on safety interpretation will be assessed.

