### **3.2 TREATMENT GROUPING**

As the starting doses in children aged between 5 and 14 years were shown to not achieve the target adult exposure, the treatment grouping originally expected - Placebo, balovaptan 4 mg equivalent and balovaptan 10 mg equivalent - is no longer tenable.

Given the numerous different dose regimens occurred in the study, as described in Table 3, the individual treatment level will be ultimately identified based on individual subject's PK exposure, estimated as the average plasma concentration ( $C_{ave}$ ) since treatment start.

$C_{ave}$  was not specifically listed in the Pharmacokinetic endpoints section of the protocol, however, in the situation of possible dose adaptations within an individual during the course of the study,  $C_{ave}$  is the PK exposure measure that reflects most realistically the individual exposure. Moreover,  $C_{ave}$  also takes into account potential dose interruptions during treatment. For subjects without dose changes or dose interruptions,  $C_{ave}$  is approximately equal to  $AUC_{0-24,ss}$  divided by 24 hrs. Individual  $C_{ave}$  will be estimated by the pharmacometrics group in Clinical Pharmacology for all subjects with at least one adequately documented PK measurement at steady-state, using a population PK modeling approach.  $C_{ave}$  at week 12 will be used as a classification factor to split the subjects receiving balovaptan into three equally sized exposure sub-groups: Low Tertile, Medium Tertile and High Tertile.

If insufficient exposure data are available for a subject and  $C_{ave}$  cannot be derived (this can happen, for example, to withdrawals or in case of issues with PK sample analyses), then his/her data will contribute to the same treatment group of the majority of his/her coetaneous taking the same regimen as per randomisation. For example, if a 6 years-old initially randomized to 1.5mg switched to 3mg and no PK data are available for him/her, then his/her data will be attributed to the Low Tertile if most of the 5-7 years-old subjects taking the same regimen are allocated, based on their available exposure, to the Low Tertile. In case no other coetaneous providing exposure data went through the same regimen pattern (as in the example, increasing dose from 1.5mg to 3mg) then data will be attributed to the same exposure sub-group of the majority of his/her coetaneous taking the same final dose (in the example, 3mg).

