This treatment grouping will be used for descriptive (ie, not inferential) statistical reporting purposes of efficacy and safety data.

For pharmacometric exploratory graphical analyses, missing PK information will not be imputed. In case of missing PK information for subjects assigned to a starting dose other than Placebo, the subject with missing PK information will be excluded from exposure-efficacy analyses.

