#### **4.2.2         Efficacy Population**

- Efficacy ITT Global

The “Efficacy Global” population consists of all subjects who gave informed consent and received at least one dose of study medication, whether prematurely withdrawn from the study or not.

Data will be summarized according to treatment classified as derived from PK exposure: Placebo, Low Tertile, Medium Tertile, High Tertile.

- Efficacy ITT Inferential

The “Efficacy ITT Inferential” population is the primary population of interest. It consists of the subset of the “Efficacy Global” population obtained by pooling data from subjects taking balovaptan 10 mg equivalent or the concurrently randomized placebo in the corresponding age band and in the same randomization stage, as highlighted in orange in Table 3, and belonging to patterns c) or d), as highlighted in yellow in Table 4. Subjects with dose adjustments or interruptions, or on a different dose than the final dose for their age group, are excluded and do not contribute to this analysis population.

Data will be summarized according to treatment classified as: Placebo, 10mg equivalent.

The following Table shows the combination of subjects' patterns (described in Table 4) to identify the Safety and Efficacy analyses population/dataset:

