**Table 5. Patterns of subjects' disposition identifying Safety and Efficacy Analysis Population/Dataset**

| Analysis Population:            | Analysis dataset:             |                                   |
|---------------------------------|-------------------------------|-----------------------------------|
|                                 | First Part (8 weeks)          | Main Part (24 weeks)              |
| Safety Global            | a + 1 st part of b | 2 nd part of b + c + d |
| Safety Inferential       | -                             | c + d                             |
| Efficacy ITT Global      | -                             | 2 nd part of b + c + d |
| Efficacy ITT Inferential | -                             | c + d                             |

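### No planned safety table shows the 4 mg eq arm, or the whole 10 mg eq arm, as randomized, although the protocol calls for it

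*SAP*

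**What the plan says.** **Protocol 6.3.1.** Everyone who took at least one dose is in the safety population, and "Data will be analyzed according to the treatment as randomized". Section 6.5 bases all safety analyses on this population, with tables by treatment.

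**SAP 4.2.1, Safety Global.** All dosed subjects are included, but "Data will be summarized according to treatment classified as derived from PK exposure", with the columns "Placebo, Low Tertile, Medium Tertile, High Tertile and All Treated with Active". SAP 3.2 defines the tertiles: average concentration since treatment start, taken at Week 12, "will be used as a classification factor to split the subjects receiving balovaptan into three equally sized exposure sub-groups". It adds that "This treatment grouping will be used for descriptive (ie, not inferential) statistical reporting purposes of efficacy and safety data".

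**SAP 4.2.1, Safety Inferential.** This is the part of Safety Global that addresses the primary efficacy objective (patterns c and d in Table 5). Here "Data will be summarized according to treatment classified as: Placebo, 10mg equivalent". SAP 4.2.2, which defines the matching efficacy population, states that "Subjects with dose adjustments or interruptions, or on a different dose than the final dose for their age group, are excluded".

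**Reason given.** SAP 3.2 explains that the starting doses missed the adult target exposure in subjects aged 5 to 14, so the three planned groups could no longer be used. SAP section 1 says that this SAP version is based on protocol Version 6. It does not mention that the safety grouping differs from 6.3.1.

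**The concern.** The two documents give different grouping rules for the same subjects. Protocol Version 6 was written with the under-exposure already known (Sections 3.3.3 and 4.4.2.1) and still kept the as-randomized rule. Missing the target exposure is a good reason to add an exposure display. It does not make the randomized arm unknown for anyone.

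Each of the three views that the SAP offers has a limitation:

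- **Tertiles** are formed after randomization. SAP 3.2 says that the average concentration takes dose interruptions into account, so an adverse event that leads to an interruption can itself move the subject to a lower tertile.
- **All Treated with Active against placebo** follows randomized assignment, but it merges both dose arms and pools stages with different active:placebo ratios (2:1 under the 1:1:1 allocation, then 1:1).
- **Safety Inferential** is by arm, but it has no 4 mg eq column. Read with SAP 4.2.2, it also drops 10 mg eq subjects who interrupted or changed dose, including any who interrupted because of an adverse event.

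At stake is whether the report can show a dose-specific safety comparison that keeps the protection of randomization.

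**Working it through.** **1. Which table shows which subjects.**

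| Subjects as randomized | Safety Global | Safety Inferential |
|---|---|---|
| Placebo | Placebo column | Placebo column, if concurrent with the included 10 mg eq subjects |
| 4 mg eq | A tertile, and pooled active | Absent |
| 10 mg eq at the final dose, no change or interruption | A tertile, and pooled active | 10 mg eq column |
| 10 mg eq, under-dosed, adjusted or interrupted | A tertile, and pooled active | Absent |

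No column holds the 4 mg eq arm, and none holds the whole 10 mg eq arm.

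**2. The plan's own planning figures.** Protocol 6.1 gives 80 evaluable subjects per arm for 80% power at one-sided 5% with effect size 0.4. Recalculation gives 81.2% power with 80 per arm, and 78 per arm needed. The earlier recruitment target also reproduces, at the 20% end of the withdrawal range: 240/(1 − 0.20) = 300. The 340 cannot be rebuilt from stated inputs, because the documents give no count of 4 mg eq or under-dosed subjects.

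**3. Size of the group outside the arm-level comparison.** Inputs: 340 recruited and 160 evaluable (SAP 2.3), and 15–20% withdrawal (Protocol 4.2.1). Outside = 340 − 160/(1 − d).

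- d = 0.15: 160/0.85 = 188.2; 340 − 188.2 = 151.8, or 44.6%.
- d = 0.20: 160/0.80 = 200; 340 − 200 = 140, or 41.2%.
- Counting only the 160 evaluable subjects as inside: 180/340 = 52.9%.

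**4. Who they are.** The number enrolled under 1:1:1 is not given. Call it M and assume a range of 100 to 250. Randomized to active = 2M/3 + (340 − M)/2, and to placebo = M/3 + (340 − M)/2. Subtract 80/(1 − d), which is 94.1 to 100 per arm.

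- M = 100: active 186.7, of whom 87–93 are outside; placebo 153.3, of whom 53–59 are outside; 4 mg eq arm 33.
- M = 250: active 211.7, of whom 112–118 are outside; placebo 128.3, of whom 28–34 are outside; 4 mg eq arm 83.

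Over this range, 87–118 active subjects (26–35% of 340) and 28–59 placebo subjects (8–17%) are outside. The 4 mg eq arm is 33–83 subjects (10–25%).

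**5. Stage mix in the pooled active column.** The share from the 1:1:1 stages is (2M/3) divided by all active, against (M/3) divided by all placebo.

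- M = 100: 66.7/186.7 = 36% against 33.3/153.3 = 22%.
- M = 175: 116.7/199.2 = 59% against 58.3/140.8 = 41%.
- M = 250: 166.7/211.7 = 79% against 83.3/128.3 = 65%.

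The mix differs by about 14 to 17 percentage points. Each 10 points of difference in event incidence between stages would therefore shift the crude pooled contrast by about 1.4 to 1.7 points with no drug effect. Stages may well differ: enrolment was staggered by age, and the first cohorts had weekly safety laboratory tests. For simplicity this step treats First Part and Main Part as one table.

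**The case against.** **The regrouping is reasoned and disclosed.** The arm labels stopped describing dose. In the Main Part, 4 mg eq covers 1.5 to 4 mg and 10 mg eq covers 3 to 10 mg, some subjects switched during treatment, and a 5–7-year-old on 3 mg could belong to either arm depending on the dosing table in force. An arm-level display averages over this and can dilute an exposure-related signal. This stands, and it is why the tertile tables should stay. It does not explain why the arm-level display is missing.

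**There is other cover.** Individual listings span Safety Global, and the monitoring committees see unblinded allocation. This also stands, but listings do not summarize incidence by arm, and committee review during the study does not replace reported tables.

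A reader might infer more than the documents support:

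- *That the 4 mg eq and under-dosed subjects are in no comparison that follows randomization.* They are: pooled active against placebo depends on assignment and not on PK. Only the arm-level split is missing.
- *That 41–45% of subjects are shown only by tertile.* Only balovaptan subjects are split. Placebo subjects stay under placebo, and every active subject is also in the pooled column.
- *That the tertile tables will show a sizeable false gradient.* The documents give no event rates by age and no exposure variability. Simulated gaps of about 2–6 points rest on assumed values for both and on a single-table layout, whereas the SAP reports First Part and Main Part separately. With about 67 subjects per tertile and incidence near 55% (both assumed), the standard error of a difference is √(2 × 0.55 × 0.45/67), about 8.6 points, so gaps of that size are below one standard error.

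**Conclusion.** The point holds as a conflict between the documents and a gap at arm level. The protocol requires all dosed subjects to be analysed as randomized. The SAP plans no safety table of the 4 mg eq arm or of the full 10 mg eq arm, and does not record the departure. About 140–152 of 340 subjects (41–45%) are outside the one arm-level comparison. That is a planning estimate. It assumes that all 340 are dosed, that withdrawn subjects remain in the inferential set, and that this set has 160/(1 − d) subjects.

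Two limits apply. The dose-change and interruption exclusion is stated in SAP 4.2.2 and reaches the safety subset because SAP 4.2.1 ties that subset to the primary efficacy objective. The colour highlighting that marks the included cells of Tables 3 and 4 cannot be seen in the text reviewed, so the exact set cannot be counted.

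The primary efficacy analysis is not affected. No size of bias in the tertile tables can be established from the documents.

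**What to change.** In SAP 4.2.1 and 4.6:

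1. Add Safety Global tables by randomized arm (placebo, 4 mg eq, 10 mg eq), at least for the Main Part. First Part tables by arm would be thin, with cohorts of about 24 adolescents and up to about 30 children.
2. Present them by randomization stage, so that 4 mg eq is set against placebo from the 1:1:1 stages only.
3. Footnote that the arm columns mix dose levels.
4. Keep the tertile tables as the exposure display.
5. State and justify any remaining departure from Protocol 6.3.1.

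Whether the tertiles become secondary, and whether risk differences with confidence intervals are added, are matters of preference. The correction does not depend on either.

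The cost is SAP wording and one more set of descriptive tables from data already held. The downside is more output, with columns that do not correspond to a single dose.

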**Table 3. Study Treatments in the 24-weeks Main Part (Study Part 2)**

| Age (yrs) | Treatments randomized (1:1:1) according to Protocol Version 1-5 |         |          | Treatments randomized (1:1:1) according to Protocol Version 5 and since 1 st Oct 2018 allowed to start as (*) or to increase to (→) the Adult dose after local IRB approval |           |               | Treatments randomized (1:1) according to Protocol Version 6 |     |          |
|-----------|---|---------|----------|--|-----------|---------------|---|-----|----------|
|           | Plc   | 4 mg eq | 10 mg eq |  | Plc       | 4 mg eq       | 10 mg eq  | Plc | 10 mg eq |
| 5-7       | Plc   | 1.5 mg  | 3 mg     | Treatment started as:  | Plc*      | 3 mg*         | 7 mg*   | Plc | 7 mg     |
|           |   |         |          | Treatment increased to:  | Plc → Plc | 1.5 mg → 3 mg | 3 mg → 7 mg   |     |          |
| 8-12      | Plc   | 2 mg    | 5 mg     | Treatment started as:  | Plc*      | 4 mg*         | 10 mg*  | Plc | 10 mg    |
|           |   |         |          | Treatment increased to:  | Plc → Plc | 2 mg → 4 mg   | 5 mg → 10 mg  |     |          |
| 13-14     | Plc   | 3 mg    | 7 mg     | Treatment started as:  | Plc*      | 4 mg*         | 10 mg*  | Plc | 10 mg    |
|           |   |         |          | Treatment increased to:  | Plc → Plc | 3 mg → 4 mg   | 7 mg → 10 mg  |     |          |
| 15-17     | Plc   | 4 mg    | 10 mg    |  | Plc*      | 4 mg          | 10 mg   | Plc | 10 mg    |

The primary study objective (balovaptan 10 mg equivalent compared to placebo) will be addressed by analyzing the dataset obtained by pooling data from subjects that took placebo or balovaptan 10 mg equivalent, as highlighted in orange in Table 3, and belonging to patterns c) or d), as highlighted in yellow in Table 4 (see Section 4. Statistical Methods for more details).

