### **2.3 DETERMINATION OF SAMPLE SIZE**

Prior to protocol version 6, a sample size of 240 subjects with ASD (80 per treatment arm) providing evaluable data at Week 24 ensured the study 80% power to detect as statistically significant, at 1-sided 5% significance level, a difference between each active dose and placebo with an effect size of at least 0.4. For the Vineland™-II 2DC score, assuming a standard deviation of about 12.5 points, then the effect size of 0.4 corresponds to 5 points. No adjustment for multiple doses was performed. Considering a withdrawal rate of around 15-20%, it was planned to recruit approximately 300 subjects overall.

In accordance to protocol version 6, 80 subjects per treatment arm (balovaptan 10 mg equivalent and placebo) are required, for a total sample size of approximately 160 subjects with ASD with evaluable data at Week 24. To achieve this number of evaluable subjects, the overall sample size in the study since it started is expected to increase to approximately 340 subjects.

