#### **4.5.3 PK/PD Analyses**

An exploratory graphical analysis of the relationship between pharmacokinetic exposure and efficacy will be performed by Clinical Pharmacology. For the exploratory graphical exposure-efficacy analyses,  $C_{ave}$  will be used either as a continuous covariate or as grouping variable. Graphical displays will include (but are not limited to) efficacy outcome measure vs. exposure by visit, and efficacy outcome measure vs. time, with trend lines split by exposure category (e.g. placebo, Low, Medium and High Tertile of  $C_{ave}$ ). The effect of subpopulations will also be investigated.

If warranted after review of initial graphical displays, a model based approach may be considered to quantify the exposure-effect relationship for Vineland™-II 2-DC. A model based exposure-efficacy analysis of other efficacy outcome measures might be considered upon agreement with the project team.

Results from pharmacometric analyses may be reported in a document separate from the clinical study report.

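### The Main Part Global tables set exposure tertiles, and for safety all active subjects, beside one placebo column pooled over randomization stages that differ in allocation, dose and age mix

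*SAP*

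**What the plan says.** SAP 4.2.1 summarizes Safety Global by "treatment classified as derived from PK exposure: Placebo, Low Tertile, Medium Tertile, High Tertile and All Treated with Active". SAP 4.2.2 uses the same placebo and tertile columns for Efficacy ITT Global, without an all-active column. SAP 3.2 forms the tertiles from average concentration at Week 12 over everyone receiving balovaptan. It explains that the original arms no longer serve because ages 5-14 fell short of the intended exposure, and it declares the grouping descriptive rather than inferential.

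For the primary population, SAP 4.2.2 restricts placebo to "the concurrently randomized placebo in the corresponding age band and in the same randomization stage". No such rule is stated for the Global populations.

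SAP Table 3 shows three treatment blocks: Versions 1-5, randomized 1:1:1; Version 5 since 1 October 2018, also 1:1:1, with subjects starting on or increased to the Table 2 doses; and "Treatments randomized (1:1) according to Protocol Version 6". The last block has no 4 mg eq arm.

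SAP Table 5 separates a First Part dataset (up to 8 weeks, first-cohort subjects) from a Main Part dataset (24 weeks). Efficacy ITT Global uses the Main Part only.

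Protocol 6.3.1 says of the safety population: "Data will be analyzed according to the treatment as randomized". For exposure-efficacy work, SAP 4.2.3 sets placebo exposure to 0, and SAP 4.5.3 plans "trend lines split by exposure category".

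**The concern.** Exposure is tied to stage. The earlier stages hold every 4 mg eq subject and every subject aged 5-14 on the lower starting doses; Version 6 holds only 10 mg eq at the updated doses. The Low tertile should therefore come almost wholly from before Version 6, and the share from Version 6 should rise across the tertiles. Placebo has its own stage mix, and because allocation moved from 2:1 to 1:1 it differs from the mix of all active subjects.

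The documents also give reasons why outcome or ascertainment might differ by stage. Enrollment was staggered, adolescents before children. The protocol synopsis has weekly hematology and CPK sampling in the first cohorts and at least four-weekly sampling later. The Version 6 amendment rationale mentions fewer CPK and more troponin T assessments. Within a stage these features apply to all arms alike; in a table pooled over stages they do not cancel.

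Exposure-response is a secondary objective, and conclusions on safety usually rest on descriptive tables of this kind.

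**Working it through.** **Yardstick.** SAP 2.3 claims "80% power to detect as statistically significant, at 1-sided 5% significance level", "assuming a standard deviation of about 12.5 points, then the effect size of 0.4 corresponds to 5 points", and states that "80 subjects per treatment arm (balovaptan 10 mg equivalent and placebo) are required". Check: n per arm = 2(1.645 + 0.842)² / 0.4² = 77.3, so 78. Power at 80 per arm = Φ(0.4 × √(80/2) − 1.645) = Φ(0.885) = 81.2%. The stated figures hold, and 5 points is a fair yardstick.

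**All active versus placebo.** Let N1 subjects be randomized 1:1:1 and N2 = 340 − N1 be randomized 1:1. The total of 340 is from SAP 2.3; the split is not given, so N1 is an assumption.

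- Early share of active = (2N1/3) / (2N1/3 + N2/2)
- Early share of placebo = (N1/3) / (N1/3 + N2/2)

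| N1 | Active | Placebo | Gap (points) |
|---|---|---|---|
| 100 | 66.7/186.7 = 35.7% | 33.3/153.3 = 21.7% | 14.0 |
| 150 | 100/195 = 51.3% | 50/145 = 34.5% | 16.8 |
| 180 | 120/200 = 60.0% | 60/140 = 42.9% | 17.1 |
| 200 | 133.3/203.3 = 65.6% | 66.7/136.7 = 48.8% | 16.8 |
| 240 | 160/210 = 76.2% | 80/130 = 61.5% | 14.7 |
| 280 | 186.7/216.7 = 86.2% | 93.3/123.3 = 75.7% | 10.5 |

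Example with N1 = 180, no drug effect, and an assumed adverse-event incidence of 40% before Version 6 and 30% under it:

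- Active: (120 × 0.40 + 80 × 0.30)/200 = 36.0%
- Placebo: (60 × 0.40 + 80 × 0.30)/140 = 34.3%

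The false difference is 1.7 points. It equals the gap times the drift and runs opposite to the drift: incidence fell over time, and active looks worse. A stage-stratified difference gives 0 in each stage and so 0 overall.

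**Primary comparison.** 10 mg eq and placebo each contribute N1/3 early and N2/2 late, so the gap is 0.

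**Tertiles.** This was simulated with no drug effect. From the documents: the doses in SAP Tables 2 and 3. Assumed: exposure proportional to dose, with the Table 2 dose giving the target; age mix 10/40/20/30% for 5-7/8-12/13-14/15-17 in every stage; between-subject CV 30-70%; and four stage splits. Results at CV 50% are below. Splits are starting doses / Version 5 at Table 2 doses / Version 6. The last column is the High-minus-Low difference per 1 unit of drift (Version 6 minus earlier).

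| Split | Version 6 share: Low / Medium / High | Placebo | High − Low |
|---|---|---|---|
| 160/40/140 | 4 / 37 / 62% | 51% | 0.58 |
| 200/40/100 | 2 / 21 / 49% | 38% | 0.48 |
| 120/60/160 | 8 / 46 / 66% | 57% | 0.58 |
| 230/50/60 | 1 / 9 / 32% | 24% | 0.31 |

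Over all splits and CVs, Version 6 supplies 0-13% of Low and 28-70% of High, and High minus Low is 0.27 to 0.69 per unit of drift. For an assumed 2-point drift in the two-domain composite, that is 2 × 0.27 = 0.5 to 2 × 0.69 = 1.4 points. A second set of assumed stage sizes (140-260 before Version 6, of whom 30-60 started on Table 2 doses) gives 0.7 to 1.5. In the first set, High minus Placebo is only 0.04 to 0.17 per unit, or 0.1 to 0.3 points for the same drift.

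The simulation leaves out mid-treatment dose increases, which would loosen the tie between exposure and stage, and any change in age mix between stages.

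**The case against.** The strongest reply is that SAP 3.2 labels the grouping descriptive. SAP 4.2.1 and 4.2.2 plan no test or interval for a tertile against placebo, and inference is confined to 10 mg eq against concurrent placebo. That stands, and it limits the consequence. It does not make the table neutral, because the layout invites exactly this comparison across columns.

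Exposure-response is also handled separately in SAP 4.5.3, which can use concentration as a continuous covariate, promises to look at subpopulations, allows a later model, and may be reported elsewhere. This stands in part: stage is not named, and placebo enters at exposure 0 with no stage term.

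SAP 3.2 openly explains why the original arms were set aside, and Safety Inferential still shows placebo against 10 mg eq. True, but no summary shows all dosed subjects by randomized arm, and 4 mg eq has no column anywhere.

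Finally, standardizing placebo cell by cell to each tertile's stage and age-band mix would be unstable. Three stages by four age bands make 12 cells for roughly 120-145 placebo subjects. That is accepted, and it is not proposed here.

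A reader might go further and infer that calendar drift will show up as an exposure-response, that the High tertile is mostly Version 6, or that the primary result is biased. The documents support none of these. They report no drift; the High tertile share runs from 28% to 70% on assumed stage sizes; and the primary comparison is 1:1 in every stage. Nor does the stage mixing reach the First Part safety tables, which hold first-cohort subjects only.

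**Conclusion.** The point holds as a limited weakness of presentation in the Main Part Global summaries and the exposure-efficacy plots. Pooling placebo over stages with different allocation, dose and age mix leaves the tertile and all-active contrasts open to any stage difference, in either direction.

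With 100 to 280 of 340 subjects assumed before Version 6, the all-active and placebo stage mixes differ by about 10 to 17 percentage points. A 2-point drift, also assumed, would put about 0.5 to 1.5 points between the High and Low tertiles, or 10 to 30% of the 5-point design effect. The stage mismatch follows from the design; its size rests on the stage sizes, age mix and exposure variability assumed above, and its effect on results depends on a drift that the documents do not report. The improvement is worth making because it is cheap.

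**What to change.** 1. **SAP 4.2.1 and 4.2.2.** Show the Main Part Global safety and efficacy tables also by randomization stage: Versions 1-5 at Table 1 doses, Version 5 after 1 October 2018, and Version 6. Define stage by protocol version and randomization date, so that placebo subjects can be classified too. In Safety Global, give all active versus placebo as a stage-stratified difference, for example with Mantel-Haenszel weights.
2. **SAP 4.2.1.** Add as-randomized columns (placebo, 4 mg eq, 10 mg eq) for all dosed subjects in Safety Global, in line with Protocol 6.3.1.
3. **SAP 4.5.3.** Stratify the exposure-efficacy plots by stage and age band, and include both in any model. Footnote that the tertiles remain confounded by age, randomized arm and clearance, which a by-stage display does not remove.

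The cost is SAP wording and programming; no new data are needed. The downside is wider tables and some small cells. With the 160/40/140 split at CV 50%, for example, the Low tertile would hold about 3 Version 6 subjects (4% of about 68), and the middle stage about 13 placebo subjects (40/3).
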